### **3.2 Exclusion Criteria**

3.21 Myeloma disease that is refractory to ixazomib treatment.

3.22 Has a known additional malignancy that is progressing or requires active treatment. Exceptions include early stage cancers (carcinoma in situ or Stage 1) treated with curative intent, basal cell carcinoma of the skin, squamous cell

carcinoma of the skin, in situ cervical cancer, or in situ breast cancer that has undergone potentially curative therapy.

3.23 Any of the following because this study involves an investigational agent whose genotoxic, mutagenic and teratogenic effects on the developing fetus and newborn are unknown:

- Pregnant women
- Nursing women
- Men or women of childbearing potential who are unwilling to employ adequate contraception

3.24 Other co-morbidity which would interfere with patient's ability to participate in trial, e.g. uncontrolled infection, uncompensated heart or lung disease.

3.25 Other concurrent chemotherapy, or any ancillary therapy considered Investigational  $\leq 14$  days prior to study registration.  
**NOTE:** Bisphosphonates are considered to be supportive care rather than therapy, and are thus allowed while on protocol treatment.

3.26 Peripheral neuropathy  $\geq$ Grade 3 on clinical examination or Grade 2 with pain during the screening period.

3.27 Major surgery  $\leq 14$  days prior to study registration.

3.28 Radiotherapy  $\leq 14$  days prior to registration. NOTE: If the involved field is small, 7 days will be considered a sufficient interval between treatment and administration of study drugs

3.29a Participation in any other clinical trials with other investigational agents not included in this trial  $\leq 21$  days prior to registration.

3.29b Has active autoimmune disease that has required systemic treatment  $\leq 2$  years prior to study registration (i.e. with use of disease modifying agents, corticosteroids or immunosuppressive drugs).  
**NOTE:** Replacement therapy (e.g., thyroxine, insulin, or physiologic corticosteroid replacement therapy for adrenal or pituitary insufficiency, etc.) is not considered a form of systemic treatment.

3.29c Has a history of (non-infectious) pneumonitis that required steroids or current pneumonitis.

3.29d Has a known history of interstitial lung disease.

3.29e Has an active infection requiring systemic therapy.

3.29f Has a history of current evidence of any condition, therapy, or laboratory abnormality that might confound the results of the trial, interfere with the subject's participation for the full duration of the trial, or is not in the best interest of the subject to participate, in the opinion of the treating investigator.

3.29g Has known psychiatric or substance abuse disorders that would interfere with cooperation with the requirements of the trial.

3.29h Is pregnant or breastfeeding, or expecting to conceive or father children within the projected duration of the trial, starting with the pre-screening or screening visit through 120 days after the last dose of trial treatment.

3.29i Has received prior therapy with an anti-PD-1, anti-PD-L1, or anti-PD-L2 agent.

- 3.29j Has a known history of Human Immunodeficiency Virus (HIV) (HIV 1/2 antibodies).
- 3.29k Has known active Hepatitis B (e.g., HBsAg reactive) or Hepatitis C (e.g., HCV RNA [qualitative] is detected).
- 3.29l Has a known history of active TB (Bacillus Tuberculosis)
- 3.29m Has received a live vaccine  $\leq$ 30 days prior to study registration.
- 3.29n Has known active central nervous system (CNS) metastases and/or carcinomatous meningitis.
- 3.29o Allogeneic hematopoietic stem cell transplant.
- 3.29p Systemic treatment with strong CYP3A inducers (rifampin, rifapentine, rifabutin, carbamazepine, phenytoin, phenobarbital), or use of St. John's wort  $\leq$ 14 days prior to registration.
- 3.29q Known GI disease or GI procedure that could interfere with the oral absorption or tolerance of ixazomib including difficulty swallowing.

#### 4.0 Test Schedule

##### 4.1 Schedule of assessments

Tests and Procedures	Days Prior to Registration		Every cycle			End of treatment
	$\leq 30$ days	$\leq 14$ days	Weekly (for first cycle) 	Day 1, Pre-treatment ( $\pm 4$ days)	Day 22, 43, 64 Pre-treatment ( $\pm 1$ day)	
Complete medical history	X					
Adverse Event monitoring		X		X	X	X
Physical exam, including weight and vital signs		X		X	X 	X
Height		X				
Performance status (ECOG scale)		X		X		X
CBC with diff.		X	X	X 	X	X
Prothrombin time (PT)	X					
Chemistry group to include sodium, potassium, glucose, alkaline phosphatase; Total and Direct bilirubin; SGOT (AST); SGPT (ALT), serum creatinine, calcium		X	X	X 	X	X
Thyroid function cascade (TSH, T3, T4, TPO antibody)	X			X	X	
LDH, Beta 2 -microglobulin, C-reactive protein, Plasma cell assessment	X					
Electrophoresis of serum and urine		X		X 	X 	X
Affected Immunoglobulin		X		X 	X 	X 
Immunofixation serum and urine	X			X 	X 	X 
Immunoglobulin free light chain		X		X 	X 	X 
X-ray skeletal survey or low dose whole body CT	X					
Bone marrow aspirate and biopsy 	X			X 	X 	X 
Research bone marrow R				X 	X 	X 
Research blood sample R				X 	X 	X 
Chest x-ray	X					
PET CT 				X 		
Pregnancy test 		X 				

Tests and Procedures	Days Prior to Registration		Weekly (for first cycle) 	Every cycle		End of treatment
	$\leq 30$ days	$\leq 14$ days		Day 1, Pre-treatment ( $\pm 4$ days)	Day 22, 43, 64 Pre-treatment ( $\pm 1$ day)	
Tests and Procedures						
Patient Medication Diary (Appendix II) 				X		X

- 1) All scheduled visits will have a window of  $\pm 4$  days unless otherwise stated
- 2) Immunofixation (IF) needed only in the absence of M-spike to document CR or sCR.
- 3) For persons of childbearing potential only. Must be done  $\leq 7$  days prior to registration and  $\leq 72$  hours prior to receiving the first dose of study drug. If the urine test is positive or cannot be confirmed as negative, a serum pregnancy test will be required.
- 4) FLC is required only if used to assess disease response during active phase
- 5) Collected prior to C1D1 treatment; at the end of 2 cycles, and to document progression or CR at any time point.
- 6) The diary must begin the day the patient starts taking the medication and must be completed per protocol and returned to the treating institution.
- 7) Affected immunoglobulin refers to the baseline M-protein type, that is, IgG, IgA, IgD, or IgM. Not applicable if patient “non-secretory” or if patient has no heavy chain, i.e. light chain myeloma.
- 8) Collected prior to C1D1 and C1D22; then every cycle prior to D1 treatment; and to document progression or CR at any timepoint.
- 9) The following testing may be done if clinically indicated: Myeloma FISH, plasma cell proliferation, and flow cytometry (MRD)
- 10) Does not need to be repeated at Cycle 1 Day 1. Baseline values can be used for Cycle 1.
- 11) If patient is stable after 2 cycles, physical exam can be decreased to Weeks 1 and 7 of each cycle.
- 12) Only if clinically indicated for MRD negative patients every 12 weeks.
- 13) Urine Electrophoresis required only if used to assess disease response.

R) Research funded (see Section 19.0). Will be charged to study and not to patient's account.

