3.12 Age  $\geq$ 18 years

3.13 The following laboratory values obtained  $\leq$ 14 days prior to registration.

- Calculated creatinine clearance (using Cockcroft-Gault equation below)\*  $\geq$ 30 mL/min
- Absolute neutrophil count (ANC)  $\geq$ 1000/mm^3
- Platelet count  $\geq$ 75000/mm^3 Note: Platelet transfusion is not allowed  $\leq$ 3 days prior to registration.
- Hemoglobin  $\geq$ 8.0 g/dL
- Total bilirubin  $\leq$  1.5 x ULN
- ALT and AST  $\leq$  2.5 x ULN

\*Cockcroft-Gault Equation:

Creatinine clearance for males =  $(140 - \text{age})(\text{actual body weight in kg}) / (72)(\text{serum creatinine in mg/dL})$

Creatinine clearance for females =  $(140 - \text{age})(\text{actual body weight in kg})(0.85) / (72)(\text{serum creatinine in mg/dL})$

3.14 Must have relapsed or refractory disease after treatments including three therapies: proteasome inhibitors, IMiDS, and anti-CD38 antibody.

3.15 Measurable disease of multiple myeloma as defined by at least ONE of the following:

- Serum monoclonal protein  $\geq 1.0$  g/dL (see Section 11.1 for definition)
- $\geq 200$  mg of monoclonal protein in the urine on 24 hour electrophoresis
- Serum immunoglobulin free light chain  $\geq 10$  mg/dL AND abnormal serum immunoglobulin kappa to lambda free light chain ratio.

3.16 ECOG performance status (PS) 0, or 1 (Appendix I).

3.17 Provide informed written consent.

3.18 Negative pregnancy test done  $\leq 7$  days prior to registration, for women of childbearing potential only.

3.19a Willing to follow strict birth control measures as detailed in Section 9.9i.

Female patients: If they are of childbearing potential, agree to one of the following:

- Practice 2 effective methods of contraception, at the same time, from the time of signing the informed consent form through 120 days after the last dose of study drug, AND must also adhere to the guidelines of any treatment-specific pregnancy prevention program, if applicable, OR
- Agree to practice true abstinence when this is in line with the preferred and usual lifestyle of the subject. (Periodic abstinence [eg, calendar, ovulation, symptothermal, post-ovulation methods] and withdrawal are not acceptable methods of contraception.)

Male patients: even if surgically sterilized (i.e., status post-vasectomy), must agree to one of the following:

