**6.13 Prior to accepting the registration, registration/randomization application will verify the following:**

- IRB approval at the registering institution
- Patient eligibility
- Existence of a signed consent form
- Existence of a signed authorization for use and disclosure of protected health information

**6.14 Documentation of IRB approval must be on file in the Registration Office before an investigator may register any patients.**

In addition to submitting initial IRB approval documents, ongoing IRB approval documentation must be on file (no less than annually) at the Registration Office [REDACTED] If the necessary documentation is not submitted in advance

of attempting patient registration, the registration will not be accepted and the patient may not be enrolled in the protocol until the situation is resolved.

When the study has been permanently closed to patient enrollment, submission of annual IRB approvals to the Registration Office is no longer necessary.

- 6.15 At the time of registration, the following will be recorded:
  - Patient has/not given permission to store and use his/her sample(s) for future research of Multiple Myeloma at Mayo.
  - Patient has/not given permission to store and use his/her sample(s) for future research to learn, prevent, or treat other health problems.
  - Patient has/not given permission for MCCC to give his/her sample(s) to researchers at other institutions.
- 6.16 Treatment on this protocol must commence at a Mayo Clinic Institution, under the supervision of a hematologist.
- 6.17 Treatment cannot begin prior to registration and must begin ≤ 14 days after registration.
- 6.18 Pretreatment tests/procedures (see Section 4.0) must be completed within the guidelines specified on the test schedule.
- 6.19 All required baseline symptoms (see Section 10.61) must be documented and graded.
- 6.19a Blood draw kit is available on site, if applicable (see Section 14).

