### 8.11 Instruction for initiation of a new cycle of therapy

A new cycle of treatment may begin on the scheduled Day 1 of a new cycle if:

- The ANC is  $\geq 1000/\mu\text{L}$
- The platelet count is  $\geq 75,000/\mu\text{L}$
- Any other non-hematologic drug-related (possible, probable, or definite) adverse event that may have occurred has resolved to  $\leq$ Grade 1 or baseline severity.

If these conditions are not met on Day 1 of a new cycle, dosing should be delayed for 1 week. At the end of that time, the patient should be re-evaluated to determine whether the criteria have been met. If the patient continues to fail to meet the above-cited criteria, delay therapy and continue to re-evaluate.

If any drug dosing was halted during the previous cycle and was restarted with a one-level dose reduction without requiring an interruption for the remainder of the cycle, then that reduced dose level will be initiated on Day 1 of the new cycle.

If any drug dosing was omitted for the remainder of the previous cycle or if the new cycle is held due to known hematologic toxicity newly encountered on the scheduled Day 1, then the new cycle will be started with a one-level dose reduction. If a new cycle of therapy cannot be restarted within 4 weeks of the scheduled Day 1 due to non-resolution of drug related toxicities, the patient will be removed from protocol therapy and will go to event monitoring.

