**Events of Clinical Interest**

Selected non-serious and serious adverse events are also known as Events of Clinical Interest (ECI) and must be recorded as such on the Adverse Event case report forms/worksheets and reported within 24 hours to the Sponsor and within 2 working days to Merck Global Safety. [REDACTED] Events of clinical interest for this trial include:

1. An overdose of Merck product, as defined above - Definition of an Overdose for This Protocol and Reporting of Overdose to the Sponsor, that is not associated with clinical symptoms or abnormal laboratory results.
2. An elevated AST or ALT lab value that is greater than or equal to 3X the upper limit of normal and an elevated total bilirubin lab value that is greater than or equal to 2X the upper limit of normal and, at the same time, an alkaline phosphatase lab value that is less than 2X the upper limit of normal, as determined by way of protocol-specified laboratory testing or unscheduled laboratory testing.\*

**\*Note:** These criteria are based upon available regulatory guidance documents. The purpose of the criteria is to specify a threshold of abnormal hepatic tests that may require an additional evaluation for an underlying etiology.

ECIs (both non-serious and serious adverse events) identified in this guidance document from the date of first dose through 90 days following cessation of treatment, or 30 days after the initiation of a new anticancer therapy, whichever is earlier, need to be reported within 2 working days to Merck Global Safety. (Attn: Worldwide Product Safety; [REDACTED] [REDACTED] regardless of attribution to study treatment, consistent with standard SAE reporting guidelines.

Subjects should be assessed for possible ECIs prior to each dose. Lab results should be evaluated and subjects should be asked for signs and symptoms suggestive of an immune-related event. Subjects who develop an ECI thought to be immune-related should have additional testing to rule out other etiologic causes. If lab results or symptoms indicate a possible immune-related ECI, then additional testing should be performed to rule out other etiologic causes. If no other cause is found, then it is assumed to be immune-related.

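### Footnote 10 of the test schedule sets no age limit of its own on first-dose CBC and chemistry, which can be up to 28 days old against 4 days under the Day 1 window

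*Combined protocol and SAP*

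**What the plan says.** The section 4.1 table schedules CBC and chemistry at screening (no more than 14 days before registration), weekly in the first cycle, on Day 1 of every cycle (pre-treatment, 4 days either way), on Days 22, 43 and 64 (pre-treatment, 1 day either way) and at end of treatment. The Day 1 entries for these two rows carry footnote 10: "Does not need to be repeated at Cycle 1 Day 1. Baseline values can be used for Cycle 1".

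The other timing rules that bear on the first dose are:

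- Section 3.13, on eligibility: "The following laboratory values obtained" no more than 14 days before registration.
- Section 6.17: "Treatment cannot begin prior to registration and must begin ≤ 14 days after registration".
- Section 4.1, footnote 1: "All scheduled visits will have a window of" 4 days either way unless stated otherwise. It is attached to the column whose heading begins "Weekly (for first cycle".
- Section 4.1, footnote 3: the pregnancy test must fall within 7 days before registration and also within 72 "hours prior to receiving the first dose of study drug".
- Section 8.11: "A new cycle of treatment may begin on the scheduled Day 1 of a new cycle if" the ANC is at least 1000/µL, platelets are at least 75,000/µL and drug-related non-hematologic events have settled.
- Section 10.81, on assessment before each dose: "Lab results should be evaluated and subjects should be asked for signs and symptoms suggestive of an immune-related event".

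**The concern.** The first dose is the only Day 1 for which the schedule drops its own recent blood count and chemistry. Later pembrolizumab dosing days all have both tests scheduled before treatment. Thyroid tests, also done at screening, are not waived on Cycle 1 Day 1.

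The population makes drift plausible. Patients have relapsed, symptomatic myeloma after a proteasome inhibitor, an IMiD and an anti-CD38 antibody. Exclusion 3.25, read as covering recent chemotherapy, reaches back only 14 days before registration. Chemotherapy that ended 15 days before registration, with labs drawn at 14 days, would satisfy both rules, and those counts might not show the full effect of that treatment.

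At stake is whether a patient whose ANC or platelets have fallen below 1000 or 75,000, or whose creatinine or liver tests have worsened, is recognised before the Day 1 doses. Those doses cannot be withdrawn: the stated half-lives are 9.5 days for ixazomib (1.3, 15.15) and about 26 days at steady state for pembrolizumab (15.25).

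**Working it through.** The plan states no lab age at first dose, so there is no figure to reproduce. The check is window arithmetic.

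**Inputs**

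| Item | Value | Source |
|---|---|---|
| a: screening labs to registration | at most 14 days | 3.13, 4.1 |
| b: registration to first dose | at most 14 days | 6.17 |
| w: Day 1 pre-treatment window | at most 4 days before the dose | 4.1 |
| Limit set by footnote 10 | none | 4.1 |

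**Age of labs at first dose**

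- Worst case with the waiver: a + b = 14 + 14 = 28 days.
- Without the waiver: w = 4 days.
- Difference: 28 − 4 = 24 days. Ratio: 28 / 4 = 7.
- Full range under the current text: 0 to 28 days. A patient dosed on the day of registration could have labs up to 14 days old.

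**Time to the next required draw.** The weekly column lists no study days. Assume the first weekly draw after dosing is nominally Day 8, so with footnote 1 it falls between Day 8 − 4 = Day 4 and Day 8 + 4 = Day 12. The longest interval between required draws is then 28 + (8 − 1) = 35 days nominally, or 28 + (12 − 1) = 39 days at the window's edge. The exposure is essentially the Day 1 doses.

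**Does another rule close the gap?**

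- The weekly column cannot be read as requiring a Day 1 draw, because footnote 10 specifically says that draw need not be repeated.
- Section 8.11 is worded for a new cycle and sets no sample age. Its ANC and platelet limits equal the eligibility limits in 3.13. Baseline counts that passed eligibility therefore pass 8.11 automatically, and the check adds nothing for the first dose.
- The ixazomib count rule in 8.3 is labelled Days 2-84.
- Section 10.81 asks for results to be evaluated, not redrawn.
- Sections 9.9b and 9.9c leave extra testing to standard clinical practice.

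None of these compels a draw before the first dose.

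**Effect on the design.** The decision rule (at least 5 successes in 14, then at least 15 in 37) does not use these labs. An exact two-stage binomial calculation gives alpha 0.0954, power 0.8526 at a 50% rate and early stopping 0.584 at a 30% rate. These match the 0.095, 0.853 and 0.584 in section 16.22, and nothing here changes them.

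**After the fix.** The maximum age at first dose becomes 4 days instead of 28.

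**The case against.** The case for leaving the footnote alone has weight. It is an explicit exception, so the protocol does not contradict itself. The 4 days is a visit window rather than a declared limit on lab age. The pregnancy-test limit serves a different purpose. Reaching 28 days needs both 14-day windows fully used in one patient. Physical exam, vital signs, ECOG status and adverse-event review stay due on Cycle 1 Day 1. Sections 9.6 and 9.9d call for fluid deficit to be corrected before study drug. Treatment starts under a hematologist at the study institution (6.16), and nobody is forbidden to redraw. All of this stands. It lowers the likely frequency and consequence, but it leaves the first-dose check to individual practice.

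A reader might also infer three stronger points that the documents do not support.

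- **That stale labs cause overdosing, or that a redraw would trigger a lower starting dose.** Section 1.3 does call a reduced starting dose appropriate in severe renal impairment and in moderate or severe hepatic impairment (unbound AUC 38% and 27% higher). But 7.1 and 8.1 give everyone 4 mg with no organ-function adjustment, and 8.11 has no clearance or bilirubin threshold. Section 1.3 also says that clearance down to 30 mL/min did not alter ixazomib pharmacokinetics. For chemistry, a fresh value informs judgment; it does not invoke a protocol rule.
- **That the adverse-event grading baseline must be redefined.** Sections 6.19 and 10.61 already require creatinine, neutrophils and platelets to be graded at baseline as part of registration. A second baseline would create ambiguity for a small gain: the stopping rule in 16.52 counts only related non-hematologic events of grade 4 or higher.
- **That lab age is unlimited.** The footnote has no limit of its own, but 3.13 and 6.17 together cap it at 28 days.

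**Conclusion.** The concern holds as a first-dose safety gap. Footnote 10 permits CBC and chemistry up to 28 days old at the first dose, where the table's own Day 1 window would allow 4, and no other text requires a newer draw. The 28 days is a worst case that follows directly from the two 14-day limits. How many patients would start on labs older than 4 days, or would have crossed a count limit meanwhile, cannot be estimated from the documents. The timing of the next draw rests on taking the first weekly visit as Day 8.

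This is an inexpensive improvement that should be made, not an error in the design. The response endpoint, alpha, power and decision rule are unaffected.

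**What to change.** Reword footnote 10 along these lines: *Baseline CBC and chemistry may be used for Cycle 1 Day 1 only if obtained within 4 days before the first dose; otherwise repeat and review before dosing, applying the ANC and platelet limits of 8.11; other abnormal values are handled at the investigator's discretion.* Leave the adverse-event grading baseline as it is.

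The cost is one routine CBC and chemistry for patients whose screening labs are older than 4 days. Thyroid tests and pre-dose research blood are already due on Cycle 1 Day 1, so no extra visit is needed. Some first doses will be held briefly. Section 8.11 uses a one-week hold and 6.17 requires treatment within 14 days of registration, so sites should not plan the first dose for the very end of that period. Eligibility is judged as of registration (13.7), so a repeat value does not make a registered patient ineligible.

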## 4.2 Event Monitoring/Survival Follow-up

	Event Monitoring Phase 				
	q. 3 months until PD or subsequent treatment for myeloma	At PD or subsequent treatment for myeloma	After PD or subsequent treatment for myeloma q. 6 months	Death	New Primary
Event Monitoring	X	X	X	X	At each occurrence

1. If a patient is still alive 2 years after registration, no further follow-up is required.

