7.5 Dexamethasone (Cycles 1-4, maximum of 1 year)

- Dexamethasone may be self-administered by the subject on an outpatient basis.
- Missed doses of dexamethasone will not be made up. Procedures for dose reductions and delays are summarized in Section 8.0.
- Dexamethasone is commercially available. Accurate records will be kept in the source documents of all drug administration (including dispensing and dosing).

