12.2 Number of lines of prior therapy: 1 vs. 2 vs.  $\geq 3$

12.3 Prior SCT: yes vs. no

### **13.0 Treatment/Follow-up Decision at Evaluation of Patient**

13.1 Patients who are sCR, CR, VGPR, PR, MR (or usCR, uCR, uVGPR, uPR, uMR), or SD will continue treatment per protocol.

13.2 Patients who develop progressive disease or start alternate therapy while receiving therapy will go to the event-monitoring phase per Section 4.2.

13.3 Patients who go off protocol treatment for reasons other than PD will go to the event-monitoring phase per Section 4.2.

13.4 Patients who are discontinued from therapy for an unacceptable adverse event(s) will be followed until resolution or stabilization of the AE(s).

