## 16.0 Statistical Considerations and Methodology

### 16.1 Overview

This is a phase II study of a novel regimen of Pembrolizumab with ixazomib and dexamethasone for treatment of relapsed multiple myeloma patients requiring therapy. This study is designed to assess the overall response rate associated with therapy with pembrolizumab added to standard doses of ixazomib and dexamethasone in patients with relapsed multiple myeloma using a single stage phase II study design with an interim analysis.

16.11 Endpoint: The primary endpoint of the trial is the overall response rate. A success will be defined as a PR or better noted as the objective status on two consecutive evaluations. Response will be evaluated using all cycles. Throughout Section 16.0, response will be considered synonymous with “success”, unless specified otherwise.

16.12 Sample Size: The single-stage study design with an interim analysis to be used is fully described below. A minimum of 14 and a maximum of 37 evaluable patients will be accrued in the phase II study unless undue toxicity is encountered. We anticipate accruing an additional 4 patients to account for ineligibility, cancellation, major treatment violation, or other reasons for a maximum of 41 patients. All patients meeting the eligibility criteria who have signed consent and received at least one dose of treatment will be considered evaluable for response, with the exception of patients who are determined to be a major violation.

16.13 Accrual Rate and Study Duration: The anticipated accrual rate is 2-3 evaluable multiple myeloma patients per month. At this rate, it will likely take about 1.5 years to enroll the patients. The maximum total study duration is expected to be approximately 4.5 years, or until the last patient accrued has been observed for at least 3 years. The earliest date anticipated for presentation of results is at approximately 2 years, or when the last patient accrued has been observed for at least 6 months.

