#### 16.32 Secondary Outcome Analyses

16.321 The  $\geq$ VGPR response rate with pembrolizumab added to Ixazomib and dexamethasone will be estimated by the number of patients who achieve a VGPR, CR, or sCR at any time divided by the total number of evaluable patients. Exact binomial 95% confidence intervals for the true success rate will be calculated.

16.322 The complete response rate with pembrolizumab added to Ixazomib and dexamethasone will be estimated by the number of patients who achieve a CR or sCR at any time divided by the total number of evaluable patients. Exact binomial 95% confidence intervals for the true success rate will be calculated.

16.323 Survival time is defined as the time from date of first treatment to death due to any cause. The distribution of survival time will be estimated using the method of Kaplan-Meier.

16.324 Progression-free survival is defined as the time from date of first treatment to the earliest date of documentation of disease progression or death due to any cause. Patients who receive subsequent treatment for myeloma before disease progression will be censored on the date of their last disease assessment prior to initiation of the subsequent treatment. Transplant will not be considered subsequent treatment. The distribution of progression-free survival will be estimated using the method of Kaplan-Meier

16.325 Adverse Events: All eligible patients that have initiated treatment will be considered evaluable for assessing adverse event rate(s). The maximum grade for each type of adverse event will be recorded for each patient, and frequency tables will be reviewed to determine patterns. Additionally, the relationship of the adverse event(s) to the study treatment will be taken into consideration.

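### Beyond month 24, required survival follow-up covers only patients still on treatment, so the later part of the overall survival curve is likely to read too high

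*Combined protocol and SAP*

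**What the plan says.** - **Section 4.2, footnote 1**, attached to the Event Monitoring Phase column heading: "If a patient is still alive 2 years after registration, no further follow-up is required".
- **Who enters that phase.** Section 13.2: "Patients who develop progressive disease or start alternate therapy while receiving therapy will go to the event-monitoring phase per Section 4.2". Section 13.3: "Patients who go off protocol treatment for reasons other than PD will go to the event-monitoring phase per Section 4.2".
- **Who does not.** Section 13.1: "Patients who are sCR, CR, VGPR, PR, MR (or usCR, uCR, uVGPR, uPR, uMR), or SD will continue treatment per protocol". These patients follow the every-cycle visits of Section 4.1, which carry no 2-year limit. Section 7.1 gives no maximum number of cycles for ixazomib or pembrolizumab; only dexamethasone has a limit, 1 year (Section 7.5).
- **Analysis, Section 16.323.** The endpoint is given as "Survival time is defined as the time from date of first treatment to death due to any cause". The estimator named for it is Kaplan-Meier, and no censoring rule or cut-off is stated for OS.
- **Planned observation, Section 16.13.** The study runs about 4.5 years, or "until the last patient accrued has been observed for at least 3 years".

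**The concern.** Kaplan-Meier assumes that patients censored at a given time have the same later risk of death as those who stay under observation. Up to month 24 the plan follows everyone. After that, a patient already off treatment needs no further contact, and one who leaves treatment later enters a phase that asks for nothing more. The patients left in the risk set are those still on protocol treatment, who are alive, without progression and tolerating therapy. If they die at a lower rate than the rest, the curve flattens for a reason that has nothing to do with the regimen.

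OS is a stated secondary goal (Section 2.22) of a single-arm study, so there is no concurrent control in which the same artificial plateau would show up. If true median survival lies beyond month 24, the reported median would be too long or not reached.

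**Working it through.** **The plan's own duration.** At 2 to 3 patients per month, 37 patients take 37/3 = 12.3 to 37/2 = 18.5 months, or about 1.5 years. Adding 3 years for the last patient gives 1.5 + 3 = 4.5 years, as Section 16.13 states. Potential follow-up is thus 36 to 54 months, so a curve past month 24 is to be expected.

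**Assumptions (none are in the documents for this regimen).** All times are exponential.
- Median progression-free survival (PFS): 6, 9, 12 or 20.6 months. The last is the figure Section 1.4 quotes for a different ixazomib combination.
- Median survival after progression: 9, 15 or 24 months.
- Death hazard before progression, d: 0.003 or 0.01 per month.
- Other treatment discontinuation: 0.01 per month.

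**Formulas.** Let λ = ln 2 / median PFS and μ = ln 2 / median post-progression survival.
- True survival: S(t) = e^(−λt) + [(λ − d)/(λ − μ)] × [e^(−μt) − e^(−λt)].
- Under the footnote, everyone at risk after month 24 is on treatment with hazard d, so the estimate tends to S(24) × e^(−d(t − 24)).

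**Worked case: PFS 9, post-progression survival 15, d = 0.003.** λ = 0.0770, μ = 0.0462, and (λ − d)/(λ − μ) = 2.403.
- S(24) = 0.1575 + 2.403 × (0.3299 − 0.1575) = 0.572
- S(36) = 0.0625 + 2.403 × (0.1895 − 0.0625) = 0.368
- Under the footnote at month 36: 0.572 × e^(−0.036) = 0.551

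Simulation of 400,000 patients gave 0.368 and 0.553. True survival crosses 50% between months 24 and 36, while the curve under the footnote still reads 0.533 at month 48.

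**Selected results from the 24 simulated combinations, month 36:**

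| Median PFS | Median post-progression survival | d | True | Under footnote | Excess (points) |
|---|---|---|---|---|---|
| 9 | 9 | 0.003 | 22.9% | 42.1% | 19.2 |
| 9 | 15 | 0.003 | 36.8% | 55.3% | 18.5 |
| 12 | 15 | 0.01 | 39.1% | 51.3% | 12.2 |
| 6 | 24 | 0.01 | 42.7% | 52.6% | 9.9 |
| 20.6 | 24 | 0.01 | 57.6% | 63.5% | 5.9 |

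The first and last rows are the extremes at month 36. At month 48 the excess runs from about 11 to 31 points. In all 24 combinations the month-24 estimates agree. Of 37 patients, about 12 to 29 are alive at month 24, but only about 2 to 13 are still on treatment.

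**Null case.** With one death hazard of 0.02 per month before and after progression, the rule gives 48.6% at month 36 against a true 48.7%. The bias comes from the difference in death rates.

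**Trial of 37.** The chance that anyone is still on treatment at month 36 is 1 − (1 − p)^37, with p = e^(−36(λ + 0.01)). For median PFS 6, 9 and 12, p = 0.0109, 0.0436 and 0.0872, giving about 33%, 81% and 97%. With a 4-month median time on treatment, a death hazard of 0.005 and no other discontinuation, p = 2^(−9) × e^(−0.18) = 0.0016 and the chance is about 6%.

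**PFS.** In a separate set of scenarios (median time on treatment 4, 6 or 12 months), in which treatment ended only through progression or death, 36-month PFS under the footnote matched the truth: 0.0016, 0.013 and 0.105.

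**The case against.** **The bias needs two conflicting passages to hold at once.** If Section 16.13 governs, everyone is observed for 3 years and nothing is biased to that point. If the footnote covers all patients, everyone is censored at 24 months and there is no later curve. Both observations are correct, and the footnote sets a minimum without forbidding further contact. But no schedule delivers 3 years of survival follow-up off treatment, voluntary contact may itself be selective, and the footnote's position ties it to the off-treatment phase. The conflict therefore has to be settled in the text.

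**Some deaths after treatment are still reported.** A reader might infer that a patient who progresses after month 24 vanishes at once. Section 10 does not support that. Deaths within 30 days of the last dose are reportable whatever the cause, as are later ones at least possibly related to treatment (10.52, 10.62). Serious events, including deaths not due to progression, are reportable to 90 days or new therapy (10.81), and new primary malignancies for at least three years (10.82). The calculation above ignores this reporting, which would trim the excess somewhat. It does not ensure capture of later deaths from progression.

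**The size is assumed, and 37 patients may leave no tail.** This stands. With short time on treatment the late curve may not exist, and where the median falls before month 24 it is untouched.

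**OS is descriptive.** No test or decision rests on it. That limits the weight of the point but does not make the late estimate valid.

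**Conclusion.** The concern holds for OS after month 24. On the natural reading of Section 4.2, censoring beyond that point depends on treatment status, and Section 16.323 does not allow for it. The upward direction needs one assumption: patients on treatment die at a lower rate than patients off it. The size cannot be fixed from the documents; 6 to 19 points at month 36 is a range under stated assumptions.

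Two wider readings are tempting. One is that the patients retained are all those without progression; in fact patients who stopped treatment for other reasons are also dropped, so those retained are only a subset. The other is that PFS is distorted in the same way and should also be cut at 24 months. No such bias is shown, and truncating PFS would discard late information from long responders for no demonstrated gain. The month-24 OS estimate, the response endpoint and the rules in Section 16.21 stand as they are. The change is worth making because it is cheap and alters what would be reported.

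**What to change.** Choose one:

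1. In Section 16.323, state that OS is censored at 24 months for every patient, including those still on treatment, and that no OS estimate beyond 24 months is reported. Count the 24 months from registration, as the footnote does, because Section 6.17 allows up to 14 days between registration and first treatment. This takes one sentence and no new data. The cost is that no OS figure past 24 months can be quoted.
2. Reconcile Section 4.2 footnote 1 with Section 16.13 so that all patients, on or off treatment, have the same end of survival follow-up. With the 3 years of Section 16.13, total duration stays at 4.5 years. The cost is survival contact with off-treatment patients beyond year 2.

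Leave Section 16.324 unchanged under either option.
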